8. The same modality used at baseline should be used throughout for imaging. CT imaging with contrast will occur every 2 cycles starting with Cycle 3 Day 1 (\pm 7 days) and should include chest, abdomen, and pelvis. Neck will be included only if measurable lesions are present. Metformin should be held prior to scans per each institutional protocol. Tumor measurements will be performed using RECIST 1.1. Progressive Disease (PD) must be confirmed by repeat scan within 8 weeks at least after 4 weeks. Patients with a known history of CNS disease must have CNS imaging at screening to rule out activity.
9. Patients will undergo a fresh tissue biopsy prior to study enrollment, unless deemed to be clinically inappropriate per PI. If not feasible, archived tissue will be used (if available).
10. The maximum time interval between registration and the first dose of study drug will be 14 days
11. Nivolumab will be given as follows:
Cycle 1-4: 240mg IV over 30 minutes (-5 / +15 minutes) every 14 days (Day 1 & 15, \pm 3 days)
Cycle 5+: 480mg IV over 60 minutes (-10 / +15 minutes) every 28 days (Day 1, \pm 3 days) until disease progression, intolerance, or withdrawal of consent.
12. Metformin will be dispensed Day 1 of each cycle. Dosing will begin at 1,000mg po once daily and escalate by 500mg every 7 days until the final dose of 2,000mg is reached. Patients will return unused drug and drug bottles at each study visit and will maintain a drug diary to track compliance.
13. The end of treatment visit should occur 30 days after the last dose of study treatment (+/- 7 days) or before starting another line of treatment, whichever comes first.
14. Correlatives from peripheral blood will be collected for all patients at Induction Day 1, C1D1, C3D1, and at the EOT. Biopsy samples (fresh or archived) will be collected for all patients if possible. See separate lab manual for specifications. See section 9.0 for details.
15. Metformin monotherapy will be given at 1,000mg PO QD during the 7-day Induction period, prior to starting nivolumab on Cycle 1 Day 1.
16. After patients come off treatment they will be followed up at 3, 6, 9, and 12 months (\pm 7 days) and then every 6 months (\pm 14 days) for 3 years for survival and progression of disease via either clinic visits or phone calls.

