9.1 Sample Collection Guidelines

Blood samples are mandatory and will be collected for Flow and Biomarker analysis at Induction Day 1, C1D1, C3D1, and EOT.

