9.3.3 T cell subpopulations

Population of CD4+, CD8+, and regulatory T cells (CD4+/CD25+) will be counted by cell sorting of PBMCs. Expression of CD4, CD8, and FOXP3 will be also examined in the tumor tissues to estimate relative ratio between T helper cells, killer T cells, and regulatory T cells.

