9.3.4 Immune and Genomic Biomarkers

To assess the dynamic change in both immune and genomic biomarkers in blood that may correlate with response to metformin. Blood will be collected prior to starting metformin, pre-dose on C1D1, C3D1, and EOT.

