PFS is defined as the time from treatment initiation to documented disease progression. OS is defined as the time from the start of treatment until death due to any cause. For patients alive at the time of data cut-off, PFS and OS will be censored as of the last tumor assessment date or known to be alive, respectively. The PFS and OS will be estimated using the Kaplan-Meier method. The number, frequency, and severity of adverse events (as defined by the NCI Common Terminology Criteria for Adverse Events or CTCAE version 4.03) will be recorded.

Baseline percent PDL1 expression, TILs (sTILs, iTILs, and their ratio), and changes in T cell subpopulations will be used as a continuous variable to predict clinical benefit or overall response rates using appropriate statistical summaries. Cox proportional hazards regression will be used to compare how these biomarkers are associated with PFS and OS as well.

Changes in these biomarkers will also be analyzed to assess for pharmacodynamic effects of treatment. Continuous variables will be analyzed using either paired t-tests (normally distributed data), signed rank tests (non-normally distributed data) or repeated measures analysis of variance (correlated normally distributed data).

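### Section 10.3 puts post-baseline T-cell changes into Cox models for PFS and OS without a visit pair or landmark, which permits biased models for the EOT change and, for PFS, the C3D1 change

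*Combined protocol and SAP*

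**What the plan says.** Section 10.3 groups baseline PD-L1, TILs and T-cell changes together. Of the last it says that "changes in T cell subpopulations will be used as a continuous variable to predict clinical benefit or overall response rates". The next sentence extends the whole group to time-to-event outcomes: "Cox proportional hazards regression will be used to compare how these biomarkers are associated with PFS and OS as well".

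Both clocks start with treatment. For PFS, "PFS is defined as the time from treatment initiation to documented disease progression"; for survival, "OS is defined as the time from the start of treatment until death due to any cause".

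The T-cell subsets are blood measurements (Section 9.3.3: "Population of CD4+, CD8+, and regulatory T cells (CD4+/CD25+) will be counted by cell sorting of PBMCs"). Section 9.1 sets the draws: "Blood samples are mandatory and will be collected for Flow and Biomarker analysis at Induction Day 1, C1D1, C3D1, and EOT". Section 9.3.4 gives the same four times for the immune and genomic markers. Section 5.0, footnote 13, places EOT 30 days after the last dose, give or take 7 days, or before the next line of treatment if that comes first. Footnote 8 puts the first on-study scan at C3D1, within 7 days either way.

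The documents do not say which two visits define a change for the Cox models. They give no landmark, no time-dependent covariate and no rule for patients without a later sample.

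**The concern.** A change from baseline does not exist at time zero. It becomes known at the later draw, and a Cox model timed from treatment start treats it as known throughout. Two of the three later draws make this a problem.

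- **EOT change.** The outcome largely sets when the sample is taken. Under Section 4.6, treatment runs until progression unless toxicity, illness or withdrawal intervenes, and EOT follows about a month later. If the marker drifts on treatment, patients with longer PFS have longer to drift, so a larger change goes with longer PFS even when the marker has no prognostic value. The same sample cannot predict response either, since response is already known when it is drawn.
- **C3D1 change, for PFS.** The draw falls at the first scan. Some patients will already have progressed, and the marker may differ because of it. The association then runs from outcome to marker.

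The association of these markers with treatment response is an exploratory objective (Section 2.3), and Section 1.3.1 presents the trial as groundwork for later ones. A false marker signal could be carried forward.

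**Working it through.** The plan gives no figure for this analysis, so there is none to reproduce. The documents also give no expected PFS or OS and no size for marker drift; those below are assumptions.

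**1. Timing.** Induction lasts 7 days and a cycle 28 days, so C1D1 is day 7 and C3D1 is 7 + 2 × 28 = day 63 from Induction Day 1. The first scan falls between days 56 and 70. The C3D1 draw can therefore come before, with or after the first documented progression.

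**2. EOT change and PFS, no true effect, n=24** (one arm). Exponential PFS, change with SD 1 plus linear drift, Cox test at two-sided 0.05. Share of trials with p<0.05:

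| Drift, SD per month | 0 | 0.05 | 0.1 | 0.2 |
|---|---|---|---|---|
| Median 4 months, exact event times | 5% | 22% | 66% | 97% |
| Median 2 months, exact event times | not quoted | 12% | 23% | 66% |
| Median 2 months, PFS dated at scans | 0% | 3% | 5% | 29% |

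If drift stops after 2 months, the rates with exact times are 5 to 8% at every drift and both medians.

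**3. EOT change, N=49** (both arms), PFS dated at day 63 and every 56 days after, Breslow ties, 1,000 runs per scenario. Hazard ratio per SD and false-positive rate:

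| Drift per 6 months | PFS, median 2 months | PFS, median 4 months | OS, median 8 months | OS, median 12 months |
|---|---|---|---|---|
| 0 | 1.01, 1.6% | 1.00, 2.5% | 1.00, 5.0% | 1.01, 4.7% |
| 0.25 SD | 0.91, 3% | 0.83, 20% | 0.95, 7% | 0.89, 10% |
| 0.5 SD | 0.84, 15% | 0.72, 65% | 0.91, 11% | 0.82, 24% |

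Scan dating creates many tied event times, and the Breslow approximation is then conservative: with no drift it rejects well below 5%. The scan-dated rates should be read against their own zero-drift rate.

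**4. C3D1 change and PFS, N=49, no drift.** With no effect of progression on the marker, rejection is 0.4% (median PFS 2 months) and 2.1% (4 months). If progression shifts the marker by 0.5 SD, the hazard ratio per SD is 1.15 with 7.6% rejection, and 1.11 with 8.6%. Adding drift gives 6.5% and 9.1%, hence about 7 to 9%. Restricting to patients progression-free after the C3D1 scan returns hazard ratios of 0.98 to 1.01 and rejection of 1 to 3% in all scenarios.

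**5. C3D1 change and OS.** The Cox partial likelihood uses only the order of events and who is at risk at each. Patients with a C3D1 sample cannot have died before it, so starting the clock at day 0 or day 63 gives the same risk sets. A numerical check agreed: log hazard ratio 0.3131 and z 1.617 both ways. With no drift or shift, the hazard ratio was 1.00 to 1.01 with 4.7 to 4.8% rejection.

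**6. C1D1 change and OS.** Hazard ratio 0.99 to 1.02, rejection 5 to 6%. For PFS, no scheduled scan falls before about day 56, so the 7-day change should precede nearly all documented progression.

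**The case against.** The strongest reply is that Section 10.3 never says a C3D1 or EOT change enters the Cox model. The only pair tied to a dynamic-change endpoint is pre-metformin to C1D1 (Section 6.5.2), which is nearly free of the problem. Section 10.3 also plans paired and repeated-measures tests of change, which give the later samples a use outside Cox. This stands as far as it goes: use of C3D1 and EOT is an inference from the sampling schedule. But nothing confines the Cox models to the 7-day change, and an analyst following the text could fit either biased model.

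A reader might infer that immortal-time bias is built in. The documents do not support that. A complete-case C3D1 change gives the same OS hazard ratio as a landmark model (step 5); the cost is that the result applies only to patients who reach C3D1. Immortal time would enter if missing changes were filled in or patients were grouped by ever having one, which the plan neither states nor excludes.

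A reader might also infer that a large share of patients progress and leave before C3D1. An exponential curve puts 1 − 0.5^((63/30.44)/median) of events before day 63: 51% at a 2-month median, 21% at 6 months. But progression must be documented, the first scheduled scan is at C3D1, and Section 4.4 allows treatment past initial progression. Those percentages do not measure lost samples, nor do they measure bias.

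Finally, the high false-positive rates need sustained drift. That is fair; the verdict is limited accordingly.

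**Conclusion.** The concern holds for two models that the text permits, not for every use of a T-cell change.

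- **EOT change:** its timing depends on the outcome. Null false-positive rates run from about 3% to 97% for PFS over assumed drifts of 0.05 to 0.2 SD per month and medians of 2 to 4 months. They are near nominal or below with no drift or an early plateau. The documents cannot narrow this range, but the plan itself tests for pharmacodynamic change, so zero drift cannot be presumed.
- **C3D1 change for PFS:** a smaller problem, about 7 to 9% if progression shifts the marker by 0.5 SD, and removed by a landmark.
- **Not affected:** baseline PD-L1 and TILs. The 7-day C1D1 change is nearly unbiased, and the complete-case C3D1 hazard ratio for OS is sound for patients who reach that visit.

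The analysis is exploratory, carries no decision rule and leaves the ORR rules alone. It should be corrected, but it does not threaten the trial's primary conclusion.

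**What to change.** Amend Section 10.3 to:

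1. Keep baseline PD-L1 and TILs as fixed covariates.
2. Name the visit pair for every change. Use Induction Day 1 to C1D1 with a C1D1 landmark.
3. Use the C3D1 change only in a landmark analysis with time counted from the landmark, or as a time-dependent covariate that takes effect after the draw. For PFS, the landmark set is patients still progression-free after the C3D1 scan.
4. Keep EOT changes for pharmacodynamic description, out of the PFS, OS and response-prediction models.
5. State whether treatment initiation means Induction Day 1 or C1D1.

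No new data are needed. The cost is fewer patients in the C3D1 analysis. With exponential PFS, 49 × 0.5^((63/30.44)/median) leaves about 24, 34, 39 or 42 of 49 patients for assumed medians of 2, 4, 6 or 9 months, and the result describes only those patients.

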4.9 Patient Replacement

If a patient is enrolled in the study but comes off study before cycle 1 day 1 of treatment, the patient may be replaced

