6.5 Exploratory end points

6.5.1 To assess the immune-related tumor and blood biomarkers including T cell markers and their association with treatment response in the above population

6.5.2 To assess the dynamic change in both immune and genomic biomarkers in blood that may correlate with response to metformin. Blood will be collected prior to starting metformin and after 7 days of metformin treatment (C1D1, pre-dose).

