10.3 Data Analyses Plans

Summary of Analytic plan for primary objective	Summary of Analytic plan for secondary objectives

Please refer to the below sample size justification for the parallel Simon's two stage design which defines how the endpoints are met.
 
For Group A. Estimated ORR for historical control is 20% versus target ORR of 40% for nivolumab and metformin combination treatment.
	
Depth of response: waterfall plot Duration and persistence of response: swimmer's plot PFS: PFS at 1 and 2 years (Kaplan-Meier analysis) OS: OS at 1 and 2 years (Kaplan-Meier analysis) ORR, DCR by irRC (descriptive statistics,

NU Study Number: NU 16L04
Other Study Number: CA 209-801

For Group B. Estimated ORR for refractory patients is 5% versus target ORR of 40% for niovulomab and metformin combination treatment.
	
exact binomial confidence intervals) We will use descriptive statistics and graphical displays to evaluate change in serum biomarkers between pre- and post-treatment. A Wilcoxon signed rank test will be used to determine if there is a statistically significant change in serum biomarkers. Toxicities will be tabulated by type and grade.

--	---

The primary analysis will be on the evaluable analysis set, including all evaluable patients regardless of drug exposure. Clinical benefit rate will be defined as stable disease (for ≥ 12 weeks), complete or partial response by both the Response Evaluation Criteria in Solid Tumors (RECIST) and irRECIST. Maximum response prior to disease progression will be used. The overall response rate will be estimated by the proportion of overall response, and its 80% confidence interval (CI) and 95% CI will be estimated using the exact binomial distribution.

Additionally, we will evaluate overall response rate, defined as complete or partial response using RECIST guidelines in a similar manner. We will also perform similar analyses using Immune Related RECIST (irRECIST). Duration of response, defined as the duration from the first documentation of clinical benefit to the first documented progressive disease or death of any cause, whichever occurs first, will also be analyzed. For patients alive and progression-free at the time of data cut off, duration of response will be censored as of the last tumor assessment date. Duration of response will only be evaluated for the subgroup of patients with a clinical benefit using the Kaplan-Meier method.

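### A four-visit repeated-measures ANOVA of blood biomarkers would keep only patients with every sample; a mixed model with named contrasts avoids this at little cost (low severity, exploratory endpoint)

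*Combined protocol and SAP*

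**What the plan says.** The sampling schedule is clear. Section 9.1: "Blood samples are mandatory and will be collected for Flow and Biomarker analysis at Induction Day 1, C1D1, C3D1, and EOT". Section 9.3.4 repeats it: "Blood will be collected prior to starting metformin, pre-dose on C1D1, C3D1, and EOT". Section 6.5.2 describes the metformin readout with the first two draws only: "Blood will be collected prior to starting metformin and after 7 days of metformin treatment (C1D1, pre-dose".

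The analysis is described twice in Section 10.3. The summary table compares pre- with post-treatment values: "A Wilcoxon signed rank test will be used to determine if there is a statistically significant change in serum biomarkers". It does not say which draw counts as post-treatment. The closing text, on pharmacodynamic effects, offers three alternatives: paired t-tests, "signed rank tests (non-normally distributed data) or repeated measures analysis of variance (correlated normally distributed data".

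Neither place names the contrasts, the analysis population for these tests, or what happens when a sample is missing.

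**The concern.** Two of the four draws can be missing for reasons tied to outcome.

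- **C3D1** falls two 28-day cycles after C1D1. A patient who dies, declines, stops for toxicity or starts other treatment before then may not give it.
- **EOT** is tied to the last dose (Table 5-1, footnote 13). Treatment is open-ended (Section 4.6), so a patient still benefiting at data cut-off has no EOT sample.

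Classical repeated-measures ANOVA needs a complete row per patient. Run on all four visits, it removes both groups from every contrast. That includes Induction Day 1 to C1D1, the only comparison on metformin alone, for which nearly everyone has both samples. If the markers move with outcome, which the exploratory objectives set out to examine, the remaining patients may not represent those treated. In a proof-of-concept trial of an immune mechanism, that readout is worth protecting.

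**Working it through.** **Inputs from the documents.** Four draws (9.1). Maximum 24 + 25 = 49 patients (10.2). C3D1 at 2 × 28 = 56 days, or 8 weeks, after C1D1. EOT about 30 days after the last dose, or before the next line of treatment if that is sooner (Table 5-1, footnote 13). No missing-sample rate, biomarker SD or significance level is given for these tests, so there is no planned figure to reproduce.

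**Assumptions.** f = share without C3D1, 10–40%. g = share without EOT because still on treatment, 0–30%. The two groups do not overlap, and early failures give the EOT draw they are due. Both arms are pooled; the plan does not say whether they will be.

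**Step 1. Who is left out by each analysis (N = 49).**

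| Analysis | Formula | Patients used |
|---|---|---|
| Pairs, Induction Day 1–C1D1 | nearly all | about 49 |
| Pairs, Induction Day 1–C3D1 | 49(1 − f) | 44 to 29 |
| Pairs, Induction Day 1–EOT | 49(1 − g) | 49 to 34 |
| Four-visit complete-case ANOVA | 49(1 − f − g) | 44 to 15 |

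The last range runs from 49 × 0.9 = 44.1 to 49 × 0.3 = 14.7.

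**Step 2. Bias of the C3D1 pairs.** Let d be the mean change in observed patients minus that in missing patients, in SD units of change. The mean over all patients is (1 − f) × observed + f × missing, so the observed mean is off by f × d.

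- d = 0: no bias.
- d = 0.5, f = 20–40%: 0.10–0.20 SD.
- d = 1, f = 20–40%: 0.20–0.40 SD.

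**Step 3. Effect on the paired t-test.** Simulation, 6,000 runs per setting, true mean change over all patients zero, two-sided 5% assumed, f = 20–40%. Rejection rates:

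| | d = 0 | d = 0.5 | d = 1 |
|---|---|---|---|
| N = 49 | 5% | 10–18% | 24–55% |
| N = 24 (one arm) | 5% | 7–11% | 13–30% |

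**Step 4. Four-visit complete cases.** Suppose mean change is d lower in early failures, and d higher in patients still on treatment, than in the remainder. The overall mean sits (g − f) × d from the remainder, and complete cases estimate the remainder, so the bias is (f − g) × d.

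- f = g = 0.3: zero.
- f = 0.4, g = 0.1, d = 1: +0.30 SD.
- f = 0.2, g = 0.3, d = 1: −0.10 SD.

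The sign depends on which loss is larger. The same deletion reaches the C1D1 contrast even though its samples exist.

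**Step 5. Illustration of the methods.** Simulation with n = 49, within-patient correlation 0.6, and true change of 0.20 SD at C1D1 and 0.40 SD at C3D1. Between 10% and 30% are lost before C3D1 (more often those with a small C1D1 change), and 10–20% are still on treatment (more often those with a large change). All of these values are assumed.

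| Method | C1D1 (true 0.20) | C3D1 (true 0.40) |
|---|---|---|
| Four-visit complete cases (24–39 of 49) | 0.25–0.40 | 0.29–0.40 |
| Pairs | 0.20 | 0.44–0.55 |
| Mixed model, all samples | 0.19–0.21 | 0.39–0.42 |

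Two variations matter. With the same losses unrelated to the marker, no method is materially biased (C3D1 0.39–0.41). With strong loss driven by the unobserved C3D1 change itself, a likelihood-based estimate gives 0.50–0.68 and pairs give 0.55–0.83, against a true 0.40.

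**The case against.** A reader might infer that early failures and on-treatment patients drop out of every planned test, that the pharmacodynamic estimate is therefore biased, and that the metformin-alone effect is distorted. The documents do not support this.

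- Both groups are lost only under a four-visit complete-case ANOVA, one of three options; the plan specifies neither the visits nor listwise deletion. Under paired tests, early failures lack only C3D1 and on-treatment patients lack only EOT.
- The metformin contrast is framed as two draws seven days apart (6.5.2). A patient who "comes off study before cycle 1 day 1 of treatment, the patient may be replaced" (4.9), so the pair should be nearly complete, and a paired test uses all of it.
- Loss at C3D1 is limited. Under Section 4.8, patients off study drug still give scheduled blood unless they withdraw consent, cannot be traced or begin other therapy. In Table 5-1, "CT imaging with contrast will occur every 2 cycles starting with Cycle 3 Day 1", the visit of the third draw, so a patient who progresses on the first scan can still give that sample. Also, "Progressive Disease (PD) must be confirmed by repeat scan within 8 weeks at least after 4 weeks", and Section 4.4 allows treatment to continue meanwhile.
- All missingness rates and effect sizes above are assumed, and the first simulation in Step 5 suits the mixed model because loss there depends on observed values.

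All of this stands, and it sets the size of the point. It does not remove it: Section 10.3 leaves the ANOVA option open without restricting the visits, and Section 4.8 stops sampling once other therapy starts, a plausible next step for early failures.

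**Conclusion.** The point holds in limited form. If classical ANOVA is run on all four draws, every contrast rests on patients who gave both C3D1 and EOT: 44 down to 15 of 49 under the assumed losses. A C3D1 paired test omits only patients lost before about week 8, and a C1D1 paired test is essentially unaffected.

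The estimates can be biased, but this is not shown. Bias requires missingness related to biomarker change, and without a missing-sample rate neither its size nor its direction can be fixed; under Step 4 it can be positive, zero or negative. Severity is low: these are exploratory endpoints with no error rate or decision attached, and the ORR analysis and two-stage rules are untouched.

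**What to change.** In Section 10.3:

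1. Replace the repeated-measures ANOVA option with a linear mixed model on all available samples: visit as a categorical factor, within-patient correlation, small-sample degrees of freedom, and a log scale for skewed markers.
2. Name two contrasts: Induction Day 1 to C1D1 (all patients with both samples) and Induction Day 1 to C3D1. Require EOT for neither.
3. Report EOT separately, as an event-driven draw taken after study drug has stopped.
4. Report the number of samples at each visit.
5. Keep the signed-rank test on pairs, already in the summary table, as a sensitivity analysis.

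The cost is a few lines of text and slightly more analysis work. The model relies on data being missing at random. If loss depends on unobserved values, it reduces the bias but does not remove it, and the report should say so.
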